4.5 Potential for Benefit

There are no direct benefits to individual subjects participating in this study, except to receive the results of the physical examination and routine lab tests to share with their personal physician. Ozone is a ubiquitous air pollutant and the main component of photochemical smog. It remains one of the most problematic air pollutants to control because it is formed from intermediates that arise from multiple sources. Inhaled ozone has been shown to irritate and damage the lung in both healthy and susceptible individuals, including children and the elderly.

This mechanistic public health research study has great potential to help us understand and ultimately prevent disease associated with common exposures such as ambient ozone.

5. Subject Recruitment and Enrollment Considerations

5.1 Subject Recruitment

Subjects will be recruited through posting flyers at approved locations on the Rutgers University Piscataway/New Brunswick campuses. Flyers will also be posted in nearby public and commercial buildings, including retail stores and community centers and made available at community events, with permission from the appropriate authority. Additionally the study will be posted on the EOHSI website (<http://eohsi.rutgers.edu/content/research-volunteers>) and the EOHSI Facebook page. Announcements about the study will be posted periodically on the EOHSI Facebook page. The announcements will link to the website. EOHSI maintains a volunteer mailing list, for persons who wish to be notified when a new study is posted on the website. An email announcement will be sent to the mailing list subscribers. Through the website and the flyers, interested candidates will be instructed to call the study coordinator. The study coordinator or a research assistant will call the subject to explain the study and answer any questions. If the candidate wishes to participate, a brief telephone screening questionnaire will be administered. The screening questionnaire will ascertain the presence of major exposure-study exclusions such as HIV infection, cardiovascular disease, stroke, diabetes, or asthma. The recruiter will ask about the COVID-19 vaccination status of the candidate, only fully vaccinated volunteers are eligible. The recruiter will inquire about a personal history of cigarette or other smoking within 5 years, regular use of vitamin E or C, selenium, or other supplements beyond a multivitamin, ingested herbal preparations, or any medication prescribed by a physician. The candidate will be asked to provide a list of his/her vitamins, supplements, and herbal preparations and their frequency of use. The supplements will be checked for antioxidant content and the candidate will be informed if he/she is eligible. If the candidate is not eligible, no identifying information will be recorded. If the candidate is eligible, contact information will be recorded and an appointment will be made for the screening visit. The candidate will be given, mailed or emailed (based on his/her preference) a copy of the consent form to review prior to the screening visit. A copy of the medical history questionnaire will also be given to the subject. The subject will be asked to bring the completed questionnaire to the screening visit. The subject will also be asked to bring proof of vaccination to the screening visit – this can be their physical vaccine card or a photo of it. If the subject is a Rutgers student or employee, they may show their myRutgers Dashboard vaccine status.

5.2 Consent Procedures

When subjects come to the EOHSI Clinical Center for screening visit, they will be provided the written informed consent to read and sign. The study coordinator or a research assistant will review the consent form with the subject and answer any questions. If the subject wishes to participate, he/she will be asked to sign the consent form. The coordinator or research assistant will also sign the consent form. A copy of the signed consent form will be given to the subject. After the consent form is signed, the medical history questionnaire will be collected and the screening visit will begin.

After the screening visits, if the subject does not meet the research criteria, the recruiter will thank the individual and explain that for safety reasons, he/she cannot participate. The specific reason will be explained. For individuals who do not become subjects, personal identification information will be removed from the screening questionnaires, although demographic information and reasons for exclusion will be maintained for research purposes. If the subject does meet the research criteria, the first exposure and follow-up visit will be scheduled.

5.3 *Subject Costs and Compensation*

No costs are expected to be incurred by the subject.

The subject will be compensated, in cash, on a pro-rated basis:

Screening visit - \$50

Exposure visit - \$125

Follow-up visit (for sputum collection) - \$75

If the subject completes all part of the study protocol, the total compensation will be \$450. Subjects will receive compensation after the completion of their screening visit, and if applicable, at the conclusion of the study, according to the pro-rated schedule above.

6. *Data Handling*

Confidentiality of participants will be protected by using identification numbers for all participants. All hard copies of forms with personal data will be kept in a locked file in a private office (Room 127) at EOHSI. All data and specimens will be coded only by the study identification number. The link to identification of all participants will be kept in a password protected file on a secure shared drive at EOHSI and will be accessible to project staff directly involved in contacting participants and the Rutgers-RWJMS Institutional Review Board. The link will be destroyed when data entry is completed. All data (consent forms, etc.) will be kept for 6 years. De-identified data will be kept indefinitely.

De-identified data will be entered into Excel worksheets. The data will be stored on the EOHSI secure shared drive. All data will be double-entered by two different investigators. All discrepancies in the data will be resolved by a third investigator. Only de-identified data will be transmitted between study investigators..

7. *Statistical Analysis*

Descriptive statistics, including means, standard deviations, and histograms will summarize the distributions of markers stratified by time point and exposure. Analysis of covariance (ANCOVA) will be used to compare the means of markers of inflammation. Specifically, with baseline level as a covariate in the model, F-tests will test whether the means are significantly different following exposure to ozone or clean air at each follow-up time-point. The mean fold-changes (or log-fold-changes if necessary to meet normality assumptions) in M1 and M2 macrophages will also be assessed at each time-point (24, 48 or 72 h) following ozone and compared to clean air in humans.

8. *Data and Safety Monitoring*

All study procedures are conducted during regular business hours when a physician is available at the EOHSI clinic. All study staff are trained in study procedures by the principal investigator. During inductions, lung function will be assessed using spirometry. A significant decrease in lung function (FEV-1<80% baseline) will be treated with albuterol. If lung function does not recover, the subject will be referred to clinical care and the adverse event will be reported to the IRB. The pulmonary fellow on call at RWJBUH is available for backup if needed. During the exposure sessions, the participants are continually observed through a window to assure that they are not exhibiting any visual signs of physical problems and wear a heart rate sensor (Polar.com) for continuous monitoring of rate. Regular voice communication between the study staff and the subject is maintained through an intercom system. A physician with a code cart is on-call during the entire procedure to respond to any subject complaints or situations. At the end of each exposure session, the subject will complete a symptom questionnaire and a spirometry. This questionnaire will be reviewed by the clinical technician and a physician to ensure that the subject is ready to resume daily activities. If a subject develops symptoms of chest pain, dizziness, or other symptoms of concern to the subject or the physician, the study will be terminated and the covering physician will examine the subject, perform an EKG, and make an appropriate triage decision, including referral to the emergency department. In the case of a delayed reaction, subjects will be instructed to call the pulmonary division of RWJMS and be given a rescue inhaler. Any respiratory reaction requiring referral to the emergency department will be considered an adverse event and will be reported to the IRB within 1 week of occurrence. Although interim analyses are not appropriate for the study, a single occurrence of an adverse event will result in a suspension of exposure visits and sputum collection while procedures are reviewed. The visits will resume only after IRB review of the event and approval of any modified procedures.

9. Reporting Results

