The study is a single blind randomized cross-over design. Subjects (up to 68 healthy men and women) will participate in the study (48 non-smokers and 10 smokers in the main study and 5-10 in the pilot study). Eligible subjects will have 5 clinic visits: one screening visit, 2 exposure visits, and 2 post-exposure sample collection visits. Each subject will participate in 2 exposure sessions, one to clean air (ozone<5ppb) and one to 0.2 ppm ozone in the Controlled Exposure Facility (CEF) at the Environmental and Occupational Health Sciences Institute (EOHSI). The order of the exposure sessions will be randomized. Up to 2 subjects may participate in each exposure session. Induced sputum samples will be collected at the baseline (during screening) then at one of three pre-selected time periods (24, 48 or 72 hours) following each exposure session. Breath, blood, oral washes, oropharyngeal swabs, and urine samples will be collected at each visit.

Subjects will undergo telephone screening. If eligible they will be scheduled for the screening visit. Subjects will be asked to refrain from antioxidants, over the counter anti-inflammatory medications, strenuous exercise, alcohol, home air purifiers, unvented household combustion sources, gases and fumes for 48 h prior to the screening visit and before each exposure visit through the post-sample collection period. Non-smokers will also be asked to avoid tobacco smoke.

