At screening, subjects will be asked to provide an induced sputum specimen (baseline sample), which will be immediately analyzed for the presence of plugs. Using the method described by Pin et al. [36] and Alexis et al., [37] subjects inhale increasing concentrations of saline (3%, 4% and 5%) for 3 consecutive 7-minute periods through a mouthpiece without a valve. To reduce the risk of bronchospasm, following the recommendations of the European Respiratory Commission [38], albuterol (180 mcg; 2 puffs of a standard metered inhaler) will be given to subjects 15 minutes prior to the start of the induction. Post-dose spirometry is performed to obtain a baseline FEV-1. The subject will be asked to breathe through his/her mouth during the induction. If the subject is observed to breathe through his/her nose, he/she will be asked to monitor his/her breathing and will be offered a nose clip to use during the induction. After each period of inhalation, an FEV-1 is measured for safety. If the FEV-1 decreases by 20% or more from the post-dose FEV-1, the procedure is stopped. After rinsing the mouth, swallowing water and blowing the nose to minimize contamination by saliva or post nasal drip, subjects will cough sputum into a sterile container. Subjects unable to provide an adequate specimen (70-75 mg of plugs) will be excused from the study. In the main study, subjects will be assigned to a post-exposure sample collection time (24, 48, or 72 hours) to be used for both exposure sessions. In the pilot study and for all smokers, all subjects will be assigned to the 24 hour post-exposure sample collection. The exposure sessions will be scheduled.

Subjects may be screened (telephone and screening visits) year-round. For the main study, the exposure visits will be scheduled between October and June, consistent with low ambient ozone months in New Jersey. For the pilot study, since only acute responses are examined (24 hours of the exposure), the screening and exposure visits will take place year-round. If over six months have passed between the screening visit and scheduling the exposures, those subjects will be re-consented and the screening visit will be repeated.

Each exposure session will be 3 hours in duration. Subjects will be called the day prior to the visit to confirm the appointment. If unable to be reached by phone, reminder texts or emails may be sent from a Rutgers-authenticated computer. Subjects will be asked to report any

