
Immediately before and after each exposure session EBC samples will be collected using the same methods as in the screening visits. In addition to the EBC samples, urine, oral washes, oropharyngeal swabs, and blood samples will be collected before and after each exposure session. During the second exposure visits, an additional blood sample will be collected for genotyping of GST polymorphisms. The urine samples will be analyzed for eicosanoids and other markers of inflammation. The blood samples will be processed by either [name] lab (research blood for future use) or the Rutgers University Cell and DNA Repository facility core at EOHSI (sample for genetic analysis).

Subjects will be asked to return for a follow-up visit either 1, 2, or 3 days after each exposure visit. Subjects will be asked to refrain from eating for 2 hours prior to the visit. The blood pressure, pulse rate, and oral temperature will be checked. IOS and spirometry will be performed and an induced sputum sample will be collected. The symptom and stress questionnaire will be administered. The blood, urine, oral washes, oropharyngeal swabs, and EBC samples will also be collected.

Sputum samples obtained after the ozone exposure may be compared with samples collected either at the screening visit or after the clean air exposure. If the subject is randomized to ozone exposure first and is unable to produce a sputum sample after the ozone exposure, the subject will be withdrawn from the study.

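### Section 7's ANCOVA names a baseline covariate without saying which value it is and states no subject term, while the pre-exposure values of EBC, urine and blood markers have no stated role

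*Protocol*

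**What the plan says.** Protocol Section 3 sets the design: "The study is a single blind randomized cross-over design". Each subject has one ozone and one clean-air session.

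Protocol Section 7 gives the model for the secondary markers: "Analysis of covariance (ANCOVA) will be used to compare the means of markers of inflammation", "with baseline level as a covariate in the model", with F-tests of ozone against clean air at each follow-up time. It names no visit for the baseline level and no subject or period term.

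On sputum, Section 3 says: "Induced sputum samples will be collected at the baseline (during screening) then at one of three pre-selected time periods". Later in the same section the screening specimen is again labelled the baseline sample. Sputum is not collected just before an exposure. The protocol's other use of the word is for the FEV-1 measured after albuterol during sputum induction, which is a safety reference.

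Other specimens do have values from each session. Section 3 states: "Immediately before and after each exposure session EBC samples will be collected using the same methods as in the screening visits", and "urine, oral washes, oropharyngeal swabs, and blood samples will be collected before and after each exposure session". It also schedules IOS and spirometry before and after exposure. EBC, urine and blood are taken at screening too. Sections 2 and 4.2 name EBC, urine and blood as specimens to be analysed for inflammatory or related markers.

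The SAP covers only the sputum M2/M1 ratio, with paired t-tests at 24, 48 and 72 hours and no baseline covariate.

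**The concern.** An EBC, urine or blood marker can have three candidate baselines: screening, pre-ozone and pre-clean-air. Section 7 does not choose among them, so the choice could be made after results are known.

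The choice matters. A screening value is constant within subject and cannot sharpen a within-subject comparison. A same-session pre-exposure value can, because it carries some of the day-to-day variation that the comparison has to overcome. If the ANCOVA is fitted as written, with no subject term, the two records of one person are treated as independent and precision from the crossover is lost. What is at stake is the precision and reproducibility of the secondary marker analyses.

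**Working it through.** **Inputs**
- n = 16 pairs per time point. Protocol Section 3.3 asks for 16 per exposure group, and Section 3's 48 main-study non-smokers over three time points give 48/3 = 16 (equal split assumed).
- Intra-person correlation ρ = 0.5, from Section 3.3.
- r, the correlation of the between-session difference in pre-exposure values with that in post-exposure values. It is not in the documents; 0.3 to 0.7 is assumed.

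**The plan's own figure.** Sixteen per group at 90% power in a two-group t-test (two-sided 0.05 assumed) corresponds to a standardised effect of 1.18. Whether the cited fold increases imply that effect depends on the size of the studies behind the 8% standard error, which is not given. The figure can be neither confirmed nor refuted. It serves here only as the number of pairs.

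**Step 1: a screening covariate within subject.** Let subject i have screening value b_i with slope β, and let τ be the ozone effect. Leaving aside period effects and error, the ozone-minus-air difference is τ + β(b_i − b_i) = τ, so b_i drops out. In one simulated 16-subject crossover (variances assumed), the estimate was 0.4212 with SE 0.1793 for the paired t-test and for the subject-effect ANCOVA with or without the screening value. A random-intercept model gave the same to four decimals.

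Exact cancellation needs complete pairs and a common slope:
- An exposure-by-baseline interaction changed the SE to 0.1754.
- With 4 of the 16 clean-air records removed, adding the covariate moved the mixed-model estimate from 0.3544 to 0.3559 and the SE from 0.2074 to 0.2033.

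**Step 2: no subject term.** Let σ be the SD of a single measurement.
- Paired: SE = σ√(2(1−ρ)/n) = σ√(1/16) = 0.250σ.
- Records treated as independent: SE = σ√(2/16) = 0.354σ, which is 1.41 times the paired SE.
- Independent records plus a screening covariate, if screening also correlates at 0.5 with each later value (an assumption): SE = σ√(2(1−0.25)/16) = 0.306σ, which is 1.22 times the paired SE.

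In the simulated data set the corresponding SEs were 0.1793 (paired), 0.2512 (independent) and 0.2511 (independent plus screening). A screening covariate may therefore recover some of the lost pairing, but not all of it under these assumptions.

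**Step 3: a same-session pre-exposure covariate.** Regressing the difference on the pre-exposure difference multiplies the variance, on average, by (1 − r²)(1 + 1/(n − 3)). At n = 16 this is (1 − r²) × 14/13.

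| r | variance factor | SE ratio | equivalent extra subjects |
|---|---|---|---|
| 0.3 | 0.91 × 14/13 = 0.980 | 0.99 | 2% |
| 0.5 | 0.75 × 14/13 = 0.808 | 0.90 | 1/0.808 = 1.24, so 24% |
| 0.7 | 0.51 × 14/13 = 0.549 | 0.74 | 1/0.549 = 1.82, so 82% |

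A simulation of 300 trials per value of r agrees: SE 0.317 against 0.352 at r = 0.5 (ratio 0.90), and 0.255 against 0.351 at r = 0.7 (ratio 0.73). The gain is an average. In the single data set of Step 1, adding a pre-exposure covariate raised the SE from 0.1793 to 0.1859.

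**The case against.** The strongest reply is that Section 7 leaves its baseline undefined. A reader might infer that the protocol defines the ANCOVA baseline as the screening sample and so discards the pre-exposure values. The documents do not support that. The screening label is attached to sputum only. For EBC, taken immediately before exposure, the same-session value is a natural reading, and no passage excludes it. This stands: the defect is an unspecified covariate, not a proven wrong one.

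Two limits of scope also stand. Section 7's ANCOVA covers inflammation markers, so it cannot be said that planned lung-function or oral-sample comparisons lose precision; no ANCOVA is stated for them. Sputum has no pre-exposure session sample, so nothing usable is being left out there.

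A further objection is carryover. The second session's pre-exposure value follows the first exposure, and the protocol states no minimum interval between sessions. If an ozone effect persisted, the covariate would be affected by treatment. This is a real condition on the method but does not decide the matter, because carryover into the second session would also contaminate the unadjusted contrast.

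Finally, chance differences between session days are not a bias when session order is randomised. That is right; the argument here is about precision and pre-specification only.

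**Conclusion.** The point holds as a specification gap with a modest, assumption-dependent cost. Section 7 does not identify its covariate and omits the subject term that a crossover needs. If the covariate is a screening value, it adds nothing to a complete-pair, common-slope contrast. If the subject term is left out, the standard error at ρ = 0.5 is roughly 1.2 to 1.4 times the paired one. Session-specific values would reduce the paired standard error by about 10% at r = 0.5, about 26% at r = 0.7 and almost nothing at r = 0.3.

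A reader might take the gain at r = 0.5 to be a third more subjects (1/0.75 = 1.33). That is the large-sample figure; at 16 pairs it is about 24%.

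A reader might also infer that the primary result is at risk. It is not: the SAP's paired t-tests on the M2/M1 ratio use no baseline covariate. Only non-primary outcomes are affected.

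**What to change.** In Section 7, or in a SAP section for the secondary markers:

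- For inflammation markers in EBC, urine or blood, state a within-subject analysis: regress the ozone-minus-air difference on the difference in same-session pre-exposure values, with a period term.
- If spirometry and IOS are to be analysed, treat them the same way.
- For sputum markers, state that the paired ozone versus clean-air contrast is used without the screening covariate, as the SAP already does for the primary ratio.
- State the assumption of no carryover into the second session's pre-exposure value.
- The SAP describes its tests in the past tense. If the data have been seen, label this analysis post hoc.

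The change needs wording only and no new samples. It costs one degree of freedom for the covariate and one for period, which leaves 13 of the paired test's 15 at 16 pairs. With period in both models the variance factor's 14/13 becomes 13/12, so at r = 0.5 the SE ratio is √(0.75 × 13/12) = 0.90, essentially unchanged. If r is low the adjustment gains little, so it should be fixed in advance rather than chosen on the results.

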3.3 Sample Size Justification

Calculations are based on published human exposure studies [41, 42] demonstrating 2.3-fold and 1.6-fold increases (SE=8%) in mean fluorescence intensity of sputum leukocyte expression of markers of M1 (CD14) and M2 (CD16) macrophages following ozone exposure at 24 h compared to clean air. The SDs for changes [the square root of $2(1-\rho)\text{SD}^2$] were calculated where rho is the intra-person correlation (0.5) between measurements. Based on this, 16 subjects/exposure group are needed to achieve 90% power using 0.05 level two-group t-tests.

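### Protocol section 7 puts M1 and M2 fold-changes on the raw scale by default, with logs conditional and no denominator defined; the log ratio should be fixed in advance

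*Protocol*

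**What the plan says.** Protocol section 7 first sets out an ANCOVA for inflammatory markers, "with baseline level as a covariate in the model". It then adds: "The mean fold-changes (or log-fold-changes if necessary to meet normality assumptions) in M1 and M2 macrophages will also be assessed at each time-point", the assessment being made "following ozone and compared to clean air in humans". It names no normality test or threshold, no test for the fold-changes, and no denominator.

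Two other places bear on the denominator. Section 3.3 uses fold in the sense of ozone relative to clean air: the cited studies are described as "demonstrating 2.3-fold and 1.6-fold increases (SE=8%) in mean fluorescence intensity", "following ozone exposure at 24 h compared to clean air". Section 3 says that post-ozone sputum "may be compared with samples collected either at the screening visit or after the clean air exposure", so the screening sample is also a permitted comparator.

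The SAP does not mention fold-changes. Its primary analysis at 24, 48 and 72 hours is a paired t-test of the M2:M1 ratio, ozone against clean air, at a significance level of 0.05.

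**The concern.** A ratio of two noisy positive measurements is right-skewed, and its arithmetic mean lies above 1 even when numerator and denominator have the same distribution. If the per-subject ozone/clean-air ratio is averaged on the raw scale and read against 1, rises are found too easily and falls are missed. The inflation grows with measurement noise, so the noisier of M1 and M2 shows the larger apparent rise.

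The conditional log adds a second difficulty. A normality check on about 16 values then decides whether an arithmetic or a geometric mean is reported, and the answer can differ between M1 and M2 or between time points.

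This matters because the SAP's ratio cannot show which cell type moved. The section 7 fold-changes are where M1 and M2 are each described separately.

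**Working it through.** **Inputs.** From section 3.3: 16 subjects per group (48 main-study non-smokers over three collection times is also 48/3 = 16), 90% power, level 0.05, planned effects of 2.3-fold (M1) and 1.6-fold (M2), and "rho is the intra-person correlation (0.5) between measurements". The documents do not give the SD, s, of the within-subject log(ozone/clean air), so s is an assumed range.

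**The plan's own figure.** A two-group t-test with 16 per group and 90% power (two-sided 0.05, sidedness assumed) needs a standardised difference of 1.18. With correlation 0.5, the SD of a change is √(2(1 − 0.5))·SD = SD. The sample size behind the SE of 8% is not given, so the 16 can be neither confirmed nor refuted. Solving backwards on the log scale from the smaller effect gives s = ln(1.6)/1.18 = 0.470/1.18 ≈ 0.40, which lies inside the range used below.

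**Null mean, reading A (per-subject ozone/clean air).** With no ozone effect the two values X and Y are exchangeable, so E[X/Y] = ½·E[X/Y + Y/X] ≥ 1, because r + 1/r ≥ 2 for any positive r. This needs no distributional assumption. For lognormal ratios, E = exp(s²/2):

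- s = 0.2: exp(0.020) = 1.020
- s = 0.3: exp(0.045) = 1.046
- s = 0.4: exp(0.080) = 1.083
- s = 0.5: exp(0.125) = 1.133
- s = 0.7: exp(0.245) = 1.278

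**False calls under reading A.** Simulated lognormal samples of 16 with no effect, t-test of the mean fold-change against 1 (assumed), nominal 2.5% in each direction. The switch column uses Shapiro-Wilk at 0.05 (assumed) to move to logs. Figures are good to a few tenths of a percentage point.

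| s | False increase, raw | False decrease, raw | False increase, with switch |
|---|---|---|---|
| 0.2 | 3.8% | 1.6% | 3.4% |
| 0.3 | 4.6% | 1.3% | 4.5% |
| 0.5 | 6.7% | 0.9% | 6.2% |
| 0.7 | 8.9% | 0.6% | 6.3% |

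The switch helps only partly because the check has little power at this size: it rejects normality in about 12%, 19%, 42% and 64% of samples at these four values of s. Always using logs holds about 2.5% in each direction.

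**Power under reading A.** For a true 30% fall at s = 0.5, power is 52% raw, about 66% with the switch, and 76% on the log scale.

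**Reading B (post-exposure/baseline after each exposure, then compared).** With a common baseline and correlation 0.5, both mean fold-changes are inflated equally (1.083 and 1.083 at s = 0.4) and their expected difference is 0. The paired test rejects in about 4% to 5% of null trials for s from 0.2 to 0.8, so there is no spurious ozone effect. For the same 30% fall at s = 0.5, power is 69% raw against 76% on logs.

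**The case against.** Section 7 never says that the fold-change is ozone over clean air. A reader might infer this from section 3.3, but that section describes published results, not this trial's estimator. The baseline sputum sample, its use as a covariate and the permitted comparison with screening all leave reading B open, and there the null bias cancels. A ratio of group means would also largely avoid it. This stands: the bias is conditional on the reading, and the undefined denominator is part of what needs repair.

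The plan names no test against 1, so the false-call rates belong to an assumed test. It also has its own safeguard, and quoting only the always-raw rates would overstate the problem, most of all at high s. Both points stand, and both sets of rates are therefore given. Under the assumed switch the excess shrinks but does not vanish.

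A reader might go further and infer that noise could produce the hypothesised M1-over-M2 pattern in the trial's main result. The documents do not support that. The SAP's primary test is a paired difference in the M2:M1 ratio, which has null mean 0 and does not inherit this bias; section 7 presents the fold-changes as an additional assessment. Inflation of 2% to 28% is also small beside planned effects of 1.6- and 2.3-fold.

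**Conclusion.** The point holds in a limited form. The text makes the raw scale the default, leaves the denominator open, and ties the log scale to a check that is unspecified and weak at 16 subjects. Under the ozone/clean-air reading, the null mean is 1.02 to 1.28 for s from 0.2 to 0.7. False increases are about 3.8% to 8.9% raw, or 3.4% to 6.3% with a normality switch, against 2.5%. Under the baseline reading there is no null bias, only lost power.

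The sizes rest on lognormal ratios, assumed values of s, an assumed t-test against 1 and an assumed Shapiro-Wilk rule; that the null mean exceeds 1 under the first reading rests on none of these. The consequence is confined to the separate M1 and M2 fold-change results, and matters most for small effects, for falls, and for comparing the size of the M1 and M2 changes. It should be corrected, but it does not threaten the primary analysis.

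**What to change.** Replace the fold-change sentence in section 7, and carry the new one into the SAP if the analysis is to be reported. For each subject, and for M1 and M2 separately, compute log(ozone/clean air) at the assigned collection time; test its mean against 0; report the geometric mean ratio with 95% CI. Delete the clause that makes logs conditional on normality.

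Add a rule for zero counts. This is the small downside: a zero after clean air already makes the raw ratio undefined, but a zero after ozone is a problem only for the log.

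The cost is one rewritten sentence and the zero rule, with no new data or visits. The SAP is worded partly in the past tense, so the analysis may already have been run. In that case the log-ratio results can be produced from the existing data and disclosed as a change to the planned analysis.
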